smoking status and for sample description. CO will be evaluated pre- and post-cigarette in each labs session, and as an outcome at Week 4 as a biomarker of changes in effects of changes in combustible product use. Urine samples will be analyzed for the tobacco-specific nitrosamine 4-methylnitrosamineo-1-(3-pyridyl)-1-butanol (NNAL), a biomarker of tobacco smoke carcinogen that decreases upon combustible tobacco cessation or reduction (Benowitz et al., 2012; Hecht et al., 2014) and total nicotine equivalents (TNEs), which is a measure of total nicotine exposure (i.e., from all nicotine-containing products). Both TNEs and NNAL will be analyzed from samples collected at baseline (BL2) and at the end of the product use period (W4). Samples will be shipped twice per year for analysis to the University of Minnesota and will be analyzed by [name]. (see letter of support included in grant application). Scores on this measure will be evaluated as an outcome at Week 4. ~~Forced Expiratory Volume (FEV) is a measure of how much air a person can exhale during a forced breath. Cigarette smoking is associated with reduced lung function in adolescents, indicating mild airway obstruction, and with slowed lung growth during adolescence (Gold et al., 1996) whereas quitting smoking leads to improvement in lung function and slows reductions in lung function associated with aging in later adulthood (Kohansal et al., 2009). Forced vital capacity (FVC) is the total volume of breath exhaled during the test; FEV1 is the volume exhaled within the first second. FEV will be measured with a water filled recording spirometer. Research assistants will be trained by Co-Investigator [name], who has experience measuring FEV in clinical settings, to take these measurements. Each participant will perform three forced expirations; FVC and FEV1 means will be calculated for each expiration judged acceptable by the RA.~~

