Cover page for Data Analysis Plan

NCT03860077

Grant number: R01DA047356

Grant Title: Impact of Nicotine Reduction on Adolescent Cigarette Use, Alternative Tobacco Use, and
Harm From Tobacco

Document date: 9/1/23

Data Analytic Approach and Power.

Overview and justification. Mixed effects models evaluated change in total cigarette use, alternative tobacco product use, study cigarette use, and biomarkers of nicotine exposure from baseline to the final study week. All analyses were with SAS V9.4 software (SAS Institute Inc., Cary, NC, USA, 2016). Due to data-collection disruptions related to the COVID-19 pandemic and intermittent data-collection challenges with the ecological momentary assessment (EMA) program, we elected to utilize the most complete data stream for primary analyses, which was Time Line Follow Back (TLFB) of outcomes collected at Week 4 and Baseline. Consistent with our prior work (e.g., ¹), aggregated timeline follow-back (TLFB) data from the final week of study cigarette use (i.e., Week 4) was compared to a one-week baseline period during which participants used usual brand cigarettes (i.e., Baseline). The mixed effect model using TLFB data was chosen over other possible analytic approaches (e.g., ANCOVA with baseline outcome covariates) to reduce bias stemming from (1) pre-randomization group differences in baseline outcome levels, and (2) missing outcome data.

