Analyses to address project aims. To address primary aims, 2-group (VLNC & NNC) x 2 repeated measures (Baseline & Week 4) mixed effects models tested the effect of the randomization group (VLNC vs. NNC) on change in cigarette use and alternative tobacco product (ATP) use from Baseline to Week 4. Similarly, to address secondary aims related to biomarkers of nicotine exposure, 2 x 2 mixed models tested the effects of VLNC vs. NNC cigarettes on change in biomarkers of nicotine exposure (i.e., total nicotine equivalents [TNEs] and cotinine), as well as average number study cigarettes smoked per day relative to average number of usual brand cigarettes smoked per day. In all models, Group (VLNC = 1; NNC = 0) was a between-subjects predictor, and Time (Baseline vs. Week 4) was the repeated measure. Subject was treated as a random effect to account for subject-level differences in baseline outcome levels. The focal tests evaluated the difference in change from Baseline to Week 4 (i.e., Time) in the VLNC vs. NNC condition (i.e., Group), which is a cross-level interactive effect of Time and Group. A *p*-value < 0.05 was interpreted as meeting statistical significance criteria. For all estimation

parameters, we report effect estimates, standard errors, and 95% confidence intervals in addition to p values.

Consistent with the original statistical analysis plan, demographics and baseline data on participant tobacco use history and individual characteristics were summarized using univariate descriptive statistics (e.g., means, standard deviations, frequencies). Data visualization and formal statistical evaluation of means, standard deviations, skewness, and kurtosis, assessed the distributional characteristics of each outcome. Where the assumptions of models implementing a normal (Gaussian) outcome distribution were not met, the statistical approach was revised accordingly. The following analytic procedures were required to meet model assumptions and account for skewed outcome distributions and low frequency events for certain outcomes.

1. Average cigarettes per day was positively skewed, with a non-normal residual distribution in a mixed model analysis specifying a normal (Gaussian) outcome distribution. Therefore, this outcome was recoded to integers and modeled as a count with a negative binomial distribution and log link.

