2. Frequencies of alternative product use (ATP) were low, particularly for combustible ATP use. Therefore, for the primary ATP outcome, combustible and non-combustible ATP use were modeled jointly and recoded as a dichotomous outcome (0 = <7 combined days of ATP use; 1 = 7+ combined days of ATP use), with a binary distribution and log link.
3. As secondary outcomes and to evaluate sensitivity, combustible and non-combustible ATP use were also considered independently as separate outcomes. Frequencies of combustible ATP use at Week 4 were too low to allow for model convergence. Frequencies of non-combustible alternative product use (ATP) were bimodal with peaks at 0 (no use) and 7 (daily use). Therefore, this outcome was recoded as a dichotomous outcome (0 = non-daily non-combustible ATP use; 1 = daily non-combustible ATP use) with a binary distribution and log link.
4. The study cigarette secondary outcome was modeled with a normal, Gaussian distribution. Baseline (Time = 0) in this analysis was average number of usual brand cigarettes at baseline,

prior to randomization, and Week 4 (Time = 1) was the average number of study cigarettes at Week 4.

5. Biomarker outcomes (i.e., total nicotine equivalents [TNEs] and cotinine) were modeled with normal, Gaussian distributions.

Missing data and sample size considerations. Missing data were assumed missing-at-random² (Whittaker, Pituch, & McDougall, 2014). Under the missing-at-random assumption, missing data for each focal variable is not expected to be related to that variable itself, e.g., a missed outcome assessment was not related to what that value would have been if it were assessed³ (Enders, 2006). The mixed model approach utilizing SAS software implemented restricted maximum likelihood estimation (continuous outcomes) and pseudolikelihood estimation (count and binary outcomes) to account for missing data. The mixed model reduces bias relative to other common approaches, particularly in cases where Group size is unbalanced due to attrition and/or baseline outcome levels differ between randomization groups.

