Original power analyses suggested a target sample size of 120 participants (60 per Group) yielded sufficient power to detect effects of Group (VLNC vc. NNC) on change in cigarettes smoked and alternative products used, as measured via ecological momentary assessment (EMA). Specified population parameter estimates were based on prior literature^{4,5} and previous studies¹, and power was calculated to reflect a small to medium effect of VLNC vs. NNC on continuous (i.e., normally distributed) outcomes. For the direct effect of Group on primary outcomes, power to detect a small to medium direct effect (estimate = .15) with 120 participants (60 per Group) was .74 with 95% coverage, where power to detect a slightly larger effect (estimate = .20) was .96, with 95% coverage. Due to unforeseeable effects of the COVID-19 pandemic on data collection and unanticipated, intermittent challenges with the EMA software, the total number of participants was reduced, as was the degree of complete EMA data. As such, TLFB were utilized for an intent-to-treat analysis, thereby retaining all participants who provided Baseline outcome data.

1. [name] RN, Tidey JW, Jackson KM, et al. The Impact of Reducing Nicotine Content on Adolescent Cigarette Smoking and Nicotine Exposure: Results from a Randomized Controlled Trial. *Nicotine Tob Res Off J Soc Res Nicotine Tob*. Published online December 9, 2022:ntac279. doi:10.1093/ntr/ntac279
3. Enders CK. A primer on the use of modern missing-data methods in psychosomatic medicine research. *Psychosom Med*. 2006;68(3):427-436. doi:10.1097/01.psy.0000221275.75056.d8

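### The SAP's two reasons for preferring the two-wave Group x Time model to ANCOVA do not hold: it is generally less precise, and for TLFB outcomes it has no bias advantage when Week 4 data are missing

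*SAP*

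**What the plan says.** The SAP's Overview and justification names ANCOVA with baseline outcome covariates as the rejected alternative. It gives two grounds for the mixed model: "to reduce bias stemming from (1) pre-randomization group differences in baseline outcome levels, and (2) missing outcome data".

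Analyses to address project aims defines the model. There are two waves and a random subject effect, and "In all models, Group (VLNC = 1; NNC = 0) was a between-subjects predictor". The test of interest is the Group x Time term: "The focal tests evaluated the difference in change from Baseline to Week 4 (i.e., Time) in the VLNC vs. NNC condition".

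Missing data and sample size considerations makes the claim again in wider form: "The mixed model reduces bias relative to other common approaches, particularly in cases where Group size is unbalanced due to attrition". Estimation is by "restricted maximum likelihood estimation (continuous outcomes) and pseudolikelihood estimation (count and binary outcomes) to account for missing data".

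On the analysis set, the same section says "TLFB were utilized for an intent-to-treat analysis, thereby retaining all participants who provided Baseline outcome data".

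**The concern.** Randomisation takes place at the end of the BL2 session, after the baseline week (Protocol section 3), so baseline differences between arms arise by chance. A Group main effect leaves each arm free to have its own baseline mean, and the Group x Time term is then a difference in change. A difference in change carries regression to the mean from any chance baseline difference. ANCOVA removes it, so the first ground points the wrong way.

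The second ground would matter if the mixed model could use outcome records that ANCOVA must drop. If every analysed participant has a baseline, the only additional records are those with a baseline and no Week 4 value.

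At stake are a wrong stated reason for the primary analysis, and precision given up in a trial whose sample fell below the planned 120. The baseline data that would recover it are already collected.

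**Working it through.** **Inputs.** From the documents: planned size 60 per group, significance at p < 0.05 (two-sided assumed), two waves, Group in all models, random subject effect, and TLFB baseline present for everyone analysed. Not given: the baseline-to-Week 4 correlation (rho), the Baseline and Week 4 SDs (s0, s1), dropout and achieved sample size. All values for these are assumptions.

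**The plan's own figure.** The SAP gives power of .74 at an estimate of .15 and .96 at .20. These belong to the original EMA-based analysis. They cannot be reproduced, because the SD, intraclass correlation and number of reports are not stated. No figure is given for the two-wave model or for its comparison with ANCOVA, and nothing below depends on the stated power.

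**Shift with chance imbalance (Gaussian).** Let D be the observed baseline difference and b = rho·s1/s0 the slope of Week 4 on baseline.

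- Change estimate = ANCOVA estimate − (1 − b)·D.
- With equal SDs the coefficient is 1 − rho: 0.5, 0.3 and 0.1 at rho 0.5, 0.7 and 0.9.
- Without stratification, one standard error of D at 60 per arm is √(2/60) = 0.183 SD. The shift is 0.091, 0.055 and 0.018 SD.

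**Precision (Gaussian, complete data).**

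- Var(change) = 2(s0² + s1² − 2·rho·s0·s1)/n.
- Var(ANCOVA) = 2·s1²(1 − rho²)/n.
- The excess is proportional to s0² − 2·rho·s0·s1 + rho²·s1² = (s0 − rho·s1)², which is never negative.
- With equal SDs the ratio reduces to 2/(1 + rho).

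| rho (equal SDs) | Variance ratio | Per-arm n to match ANCOVA with 60 | Power where ANCOVA has 80% |
|---|---|---|---|
| 0.5 | 1.33 | 80 | 68% |
| 0.7 | 1.18 | 71 | 73% |
| 0.9 | 1.05 | 63 | 78% |

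Power is Φ((1.96 + 0.84)/√ratio − 1.96). At rho 0.5 this is Φ(2.80/1.155 − 1.96) = Φ(0.47) = 0.68.

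Equal SDs matter to these sizes:

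- s1/s0 = 1.3, rho 0.7: (1 + 1.69 − 1.82)/(1.69 × 0.51) = 0.87/0.862 = 1.01, with shift coefficient 1 − 0.91 = 0.09.
- s1/s0 = 0.6, rho 0.6: (1 + 0.36 − 0.72)/(0.36 × 0.64) = 0.64/0.2304 = 2.78, with shift coefficient 1 − 0.36 = 0.64.

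**Missing Week 4, complete baselines (Gaussian simulation, 60 per arm).** With equal SDs and 27–29% of Week 4 missing in a way that depends on baseline, the random-intercept model and ANCOVA both had absolute bias of at most 0.010 SD. ANCOVA was usually still the more precise. Across 12 dropout scenarios the ANCOVA/mixed-model variance ratio was 0.79–0.99, except for one value of 1.02 at rho 0.9.

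The random intercept also imposes one variance at both waves. It therefore works with a slope near 2·rho·s0·s1/(s0² + s1²) instead of rho·s1/s0. At rho 0.6:

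- s1/s0 = 0.8: 0.96/1.64 = 0.59 against 0.48.
- s1/s0 = 0.6: 0.72/1.36 = 0.53 against 0.36.

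If dropout depends on baseline in opposite directions by arm, this gap becomes bias. It was about 0.08 and 0.14 baseline SD at those two ratios, with ANCOVA within 0.005. Runs with somewhat different assumed dropout gave 0.09 at ratio 0.8, and 0.12 and 0.16 at ratio 0.6.

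**Cigarettes per day (negative binomial).** A maximum-likelihood simulation (60 per arm, assumed means of about 8 and 7 per day, complete data) compared the Group x Time model with a regression on log baseline. The variance ratio was 1.35 and 1.14 at observed log-scale correlations of 0.36 and 0.55. The slope on imbalance was −0.61 and −0.36, against −0.05 and +0.01. With dropout dependent on baseline and differing by arm, the ratios were 1.25 and 1.13, and both methods averaged within about 0.01 of the true value of zero. A separate pseudolikelihood simulation, which compared the SAP model with a common-baseline model on complete data, agreed in direction.

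**Binary ATP (log link).** A random-intercept pseudolikelihood fit succeeded too rarely (0–82 of 150 trials) to give a size.

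**The case against.** The strongest reply is that the simple results, a shift of −(1 − rho)·D and a ratio of 2/(1 + rho), need equal SDs. The documents do not state this, and neither primary outcome is analysed as Gaussian. This stands. The table is a set of examples and not a range for this trial, the negative binomial sizes depend on parameters the documents do not give, and no size is available for binary ATP. The direction survives for complete Gaussian data at any SDs, and the count simulations agree with it.

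Second, stratification on cigarettes per day and on both kinds of ATP use (Protocol section 6e) limits imbalance. This also stands. With 16 strata and an assumed block size of four, the one-standard-error shift falls to 0.06–0.09, 0.04–0.05 and 0.01–0.02 SD at rho 0.5, 0.7 and 0.9. Power under the same assumptions barely changes (68–69%, 74% and 78%), because no model in the SAP names the stratification factors.

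Third, the missing-data reason could be read as a defence of TLFB over EMA. The sentence names ANCOVA as the alternative, so that reading does not fit. The broader sentence in the missing-data section is defensible against other methods. In the dropout simulations, completer change scores were biased by 0.03–0.25 SD, unadjusted completer comparisons by 0.13–0.44 and last observation carried forward by 0.14–0.29.

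A reader might infer that the primary test is invalid or that the trial's results are biased. The documents do not support that. The change test is unbiased over randomisation, and the dropout bias above needs unequal SDs together with arm-specific dropout related to baseline, neither of which is reported. Nor does the point carry over in full to the biomarkers. They rest on urine collected at BL2 and Week 4 (Protocol section 11d), and if a baseline sample is missing the mixed model can use a Week 4 record that plain ANCOVA drops.

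**Conclusion.** The concern holds as a false rationale and a probable loss of precision, not as a fault in validity. Given a chance baseline difference, the Group x Time estimate moves by −(1 − rho·s1/s0)·D in the Gaussian case. Its complete-data variance is at least that of ANCOVA: 5% to 33% larger for rho between 0.9 and 0.5 with equal SDs, and anywhere from almost no excess to well over double with the unequal SDs tried. For TLFB outcomes the model has no bias advantage over ANCOVA when Week 4 is missing, and under unequal SDs with arm-specific dropout it can do worse. For cigarettes per day the direction is supported but the size is not fixed; for binary ATP no size is shown. The loss in this trial cannot be computed, and it is small if rho is high and the SDs are similar.

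**What to change.** **Wording.** Delete the claim of less bias than ANCOVA from the Overview and justification. In the missing-data section, name the approaches that the bias statement covers (completer change score, unadjusted completer comparison, last observation carried forward) and make clear that ANCOVA is not among them.

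**Analysis.** The SAP is written in the past tense, so present this as a post hoc re-analysis beside the existing result and not in place of it.

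- *Cigarettes per day and biomarkers:* a baseline-adjusted Week 4 comparison. Either use baseline as a covariate, or use a common baseline mean by dropping the Group main effect and keeping Time and Group x Time. The common-baseline form also keeps Week 4-only records. For Gaussian outcomes, let the variance differ by wave.
- *Binary ATP:* a Week 4 model with baseline as a covariate, where it converges.
- *Optional:* add the four stratification factors where the model converges.

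**Cost.** A re-run, the post hoc label, and possible non-convergence for sparse ATP outcomes. The SAP already reports this for combustible products: "Frequencies of combustible ATP use at Week 4 were too low to allow for model convergence". No new data are needed.

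### NNAL is a current secondary outcome in the protocol, but the SAP neither models it nor says why

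*SAP*

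**What the plan says.** **Protocol.** Section 11 has toxicant exposure among the secondary outcomes and names two measures for it, TNEs and NNAL. The spirometry entry on the next line is struck through; NNAL is not. Section 11d plans both urine assays from samples taken at Baseline 2 (BL2) and Week 4, and Table 1 has a row for urine NNAL/TNEs. Section 11d also says what each measures: TNEs reflect nicotine from every nicotine-containing product, while NNAL marks exposure to a tobacco smoke carcinogen and falls when combustible use stops or is cut. The Aim 2 hypothesis in Section 2a covers nicotine exposure and toxicant exposure together.

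**SAP.** The overview describes models for cigarette use, alternative tobacco product (ATP) use, "study cigarette use, and biomarkers of nicotine exposure from baseline to the final study week". The section on project aims introduces the biomarker models "to address secondary aims related to biomarkers of nicotine exposure" and defines these as "change in biomarkers of nicotine exposure (i.e., total nicotine equivalents [TNEs] and cotinine". Item 5 of the analytic procedures repeats the same pair: "Biomarker outcomes (i.e., total nicotine equivalents [TNEs] and cotinine) were modeled with normal, Gaussian distributions". NNAL is not mentioned.

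**The concern.** The protocol's outcome list was edited and NNAL was kept, so it should be accounted for in the analysis plan. The SAP instead closes its biomarker list at TNEs and cotinine, both labelled as nicotine exposure, and does not say that NNAL was dropped, deferred or unavailable.

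At stake is one part of Aim 2. Participants may use e-cigarettes and other nicotine products throughout (protocol Sections 3 and 6c). On the protocol's own definitions, a change in total nicotine is therefore not a measure of change in smoke-carcinogen exposure. The Lay Summary names toxicant exposure in young users as an evidence gap. A reader of the SAP cannot tell whether NNAL was never assayed, assayed in part, or assayed and left out.

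**Working it through.** No sample size, power or error-rate figure bears on this point. The check sets the protocol's outcome list beside the SAP.

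**Step 1: the current secondary list.** With the struck spirometry entry removed, Section 11 has two bullets naming four measures.

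| Secondary measure (protocol Section 11) | Model in SAP? | Reason given if not? |
|---|---|---|
| Combustible ATP use | No | Yes, item 3 |
| Non-combustible ATP use | Yes, item 3 | – |
| TNEs | Yes, aims section and item 5 | – |
| NNAL | No | No |

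Two modelled + one explained + one with neither = four. NNAL is the only measure in this list with neither a model nor an explanation.

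**Step 2: is the SAP's biomarker list open or closed?** Both places that name the biomarkers introduce them with i.e., not e.g. The list therefore reads as complete. The words NNAL, toxicant and carcinogen each occur 0 times in the SAP.

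**Step 3: do the SAP's stated reasons reach NNAL?** The SAP explains three other departures:

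- The move to timeline follow-back data is explained by "Due to data-collection disruptions related to the COVID-19 pandemic and intermittent data-collection challenges with the ecological momentary assessment (EMA) program". That sentence concerns the data source for the primary analyses.
- The missing combustible ATP model is explained: "Frequencies of combustible ATP use at Week 4 were too low to allow for model convergence".
- The data loss is disclosed: "the total number of participants was reduced, as was the degree of complete EMA data".

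None mentions NNAL or urine assays.

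**Step 4: would the existing model accommodate NNAL?** The SAP's models compare two groups at two times, Baseline and Week 4. Section 11d plans NNAL at BL2 and Week 4, so the design matches without change.

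**Step 5: outcomes in the SAP that the protocol list does not contain.** Cotinine is modelled under the secondary aims, but the supplied protocol uses it only for screening (Section 4a and the smoking inclusion criterion in Section 4b). Item 4 models a study-cigarette secondary outcome that Section 11 does not list separately either.

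**Step 6: is NNAL the only biomarker without a model?** No. Section 11d also describes breath carbon monoxide (CO) as a Week 4 outcome, and the SAP has no model for it. CO is not in the Section 11 list, so the statement in Step 1 holds for that list only.

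**The case against.** The strongest case on the other side has five parts.

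- **An earlier plan may cover NNAL.** The SAP refers to an original statistical analysis plan that was not supplied. This limits what can be inferred, but the SAP cites that plan only for the descriptive summaries. A cross-reference would settle the matter, and there is none.
- **NNAL may never have been assayed.** This is possible. It would make the remedy a disclosure rather than an analysis; it would not make the silence adequate.
- **Toxicant exposure is partly covered.** This stands. A reader might infer that the toxicant half of Aim 2 has no biomarker test at all. The documents do not support that, because Section 11 itself places TNEs under toxicant exposure and TNEs are modelled. What lacks a test is the smoke-carcinogen marker as Section 11d defines it.
- **Modelled TNEs do not prove that NNAL data exist.** This also stands. Both were planned from the same visits, but the documents do not say that they share an assay, specimen volume or budget. The omission does not depend on that argument.
- **The exploratory outcomes have no models either.** True, but the protocol ranks NNAL above them, and the SAP says that it addresses secondary aims.

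A reader might also infer selective reporting. Nothing in the documents shows that NNAL results were seen or suppressed, and none is alleged here.

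**Conclusion.** The gap is real and narrow. One of the four measures in the protocol's current secondary list, NNAL, has neither a model nor a reason in the supplied SAP, so the smoke-carcinogen part of the Aim 2 exposure hypothesis is untested under the SAP as written. The count treats the two remaining bullets as four measures; counted as bullets, each is partly addressed.

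This rests on three readings: struck text in the protocol is withdrawn and un-struck text is current; i.e. closes the biomarker list; and the supplied SAP is the plan that governs the analysis. Confidence is high for the textual gap. Nothing can be said about its consequence for results, because the documents do not show whether NNAL was assayed. No numerical bias is claimed, the primary outcomes are unaffected, and the SAP draws no toxicant conclusion from TNEs or cotinine. It should be fixed, because a named secondary outcome is unaccounted for.

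**What to change.** 1. **If NNAL results exist:** fit the SAP's existing two-group by two-time mixed model to NNAL at BL2 and Week 4, after the distribution check that the SAP already applies to each outcome, using the log scale if the values are skewed. Report it in the SAP's own format: "we report effect estimates, standard errors, and 95% confidence intervals in addition to p values". Cost: one more run of an existing model, one SAP item and one result row.
2. **If NNAL was not assayed, or only in part:** say so, give the reason and the number of BL2 and Week 4 samples assayed per group, and state that carcinogen exposure by NNAL was not tested. Cost: one or two sentences and a small count table.
3. **Unlisted outcomes:** label cotinine and the study-cigarette secondary outcome as not in the protocol's Section 11 list, or cite the plan that lists them. Cost: a wording change.

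No new assays are asked for.
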